2 STUDY OBJECTIVES

Primary objective:

To investigate the comparative bioavailability of edaravone oral suspension administered orally and via a nasogastric tube in healthy adult subjects

Secondary objective:

To investigate the pharmacokinetics, safety, and tolerability of a single dose of edaravone oral suspension in healthy subjects

3 SUBJECTS

3.1 Subjects

Healthy adult subjects

3.2 Inclusion Criteria

Subjects who meet all of the following criteria and who have the capability of giving informed consent will be included in the study.

- (1) Healthy adult male or female volunteers
- (2) Japanese*
- (3) Subjects aged between 20 and 45 years at the time of informed consent
- (4) Subjects who have thoroughly understood the contents of the study and voluntarily provided written informed consent to participate in the study

Definition of Japanese*: People born in Japan whose parents and grandparents are Japanese and who have not lived abroad for 10 years or longer

[Rationales for setting]

Regarding (1), (2), and (3), age-restricted healthy adult volunteers were selected as the study population to ensure uniform subject backgrounds as far as possible and for this study to conform with the “Guideline for Bioequivalence Studies of Generic Products” (PFSB/ELD Notification No. 0229-10 dated February 29, 2012) [1] and the Guidance for Industry, Bioavailability and Bioequivalence Studies Submitted in NDAs or INDs - General Considerations (March 2014) [2], which specify that the subjects should be healthy adult volunteers in principle. In addition, the subjects were limited to Japanese in order for PK to be evaluated in Japanese.

- (4) To observe the provisions for subject protection in the Guidelines for Good Clinical Practice (GCP).

3.3 Exclusion Criteria

Subjects who meet any of the following criteria between screening and investigational product administration will be excluded from the study.

- (1) Subjects with a current or previous history of cardiac, hepatic, renal, gastrointestinal, respiratory, psychiatric/nervous, hematopoietic, or endocrine diseases, and those whom the investigator (or subinvestigator) deems unsuitable for the study

- (2) History of drug or food allergies
- (3) History of alcohol or drug abuse or dependence
- (4) Body mass index (BMI) of <18.0 or >30.0, or a body weight of <50 kg
(BMI formula: body weight [kg]/height [m]², rounded to one decimal place)
- (5) Subjects who test positive for hepatitis B surface antigen, serological test for syphilis, hepatitis C virus antibody, or human immunodeficiency virus antigen/antibody at screening, or for COVID-19 virus at Day -1
- (6) Any clinically significant 12-lead ECG abnormality or QTcF interval \geq 450 msec
- (7) Blood donation or sampling with a total volume of \geq 400 mL within 12 weeks, \geq 200 mL within 4 weeks, or \geq 800 mL within one year before providing informed consent
- (8) Blood component donation or blood sampling within 2 weeks before providing informed consent, or blood donation and transfusion from informed consent to the start of investigational product administration
- (9) Subjects who have undergone any surgery known to affect the gastrointestinal absorption of drugs (except for appendectomy and herniotomy)
- (10) Female subjects of childbearing potential who do not agree to use an effective method of contraception from screening or 2 weeks before the start of investigational product administration, whichever comes earlier, to 14 days after the completion (or discontinuation) of investigational product administration. Male subjects who do not agree to use an effective method of contraception from the start of investigational product administration to 14 days after the completion (or discontinuation) of investigational product administration
- (11) Subjects who have previously received edaravone
- (12) Subjects who have participated in another clinical study and received an investigational product within 12 weeks before providing informed consent
- (13) Subjects who have used any drugs other than the single use of acetylsalicylic acid within 7 days before the initiation of investigational product administration
- (14) Use of alcohol or any products containing xanthin or caffeine within 24 hours before screening and visit on Day -1
- (15) Use of any nutritional supplement(s) within 7 days before the initiation of investigational product administration
- (16) Use of grapefruit, grapefruit juice, or any processed food(s) containing these substances within 24 hours before screening and visit on Day -1

- (17) Use of any tobacco or nicotine-containing product(s) within 24 hours before screening and visit on Day -1
- (18) Female subjects who have a positive pregnancy test at screening and on Day -1, are pregnant or breast feeding, or plan to get pregnant during the study
- (19) Subjects with a history of reconstructive nasal surgery, or any evidence of deformities or asymmetry of the nose, non-patent nares/obstructed nasal airway, or the presence of nasal ulcers or polyps that would prevent an adequate NGT insertion.
- (20) Subjects judged by the investigator (or subinvestigator) to be unsuitable for the study for any other reason

[Rationales for setting]

- (1) was set to ensure the safety of subjects and to exclude unhealthy subjects.
- (2), (3), (5), (6), and (20) were set to perform the study safely and ethically.
- (4) was set to reduce PK variability due to difference in BMI between subjects.
- (7) and (8) were set to ensure the safety of subjects regarding the volume and interval of blood sampling, in reference to the "Enforcement Regulations for the Act on Securing a Stable Supply of Safe Blood Products."
- (9), (13), (15), (16), and (17) were set to avoid possible effects on PK assessment.
- (10) and (18) were set to assure safety although no toxicity findings were observed at the highest dose of 200 mg/kg in the reproductive and developmental toxicity studies.
- (11) and (14) were set to avoid possible effects on the assessment of this study.
- (12) was set to perform the study safely and ethically and avoid unpredictable effects of a drug whose efficacy and safety profile has not been established.
- (19) was set to avoid possible effects on the conduct of the study.

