8.2 Subject Enrollment

After closing the contract between the study site and the sponsor, and the start of the study period specified in the contract, the investigator (or subinvestigator) will conduct the observations and tests (see "9 Tests and Observations") for subjects who have provided written informed consent within 30 days before starting administration of the investigational drug. The investigational drug will be administered to subjects who meet all of the inclusion criteria and none of the exclusion criteria. If any abnormal finding is detected in any subject during the observations and tests prior to the start of the investigational drug administration, that subject will be examined from a medical point of view to ensure the safety of the subject and to examine whether there is no concern regarding the safety assessment of the study drug. If a retest is required to make a medical judgment, the retest will be performed after an appropriate interval. If the finding is judged to be of no concern from a medical point of view, the investigator (or subinvestigator) will record the reason for the judgment in the source data before administering the investigational drug to the subject. If any subject is excluded due to ineligibility prior to investigational drug administration, the investigator (or subinvestigator) will record the reasons in the subject screening log, and replace the excluded subject with a reserve subject.

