8.4 Duration of Dosing

Single-dose: Dosing once each on Period I and II.

[Rationales for setting]

In accordance with the “Guideline for Bioequivalence Studies of Generic Products” (PFSB/ELD Notification No. 0229-10 dated February 29, 2012)[1] and Guidance for Industry: Bioavailability and Bioequivalence Studies Submitted in NDAs or INDs - General Considerations (March 2014)[2], the subjects will receive a single dose.

8.5 Prohibited Matters Before and During the Study Period**8.5.1 Prohibited Matters****(1) Use of medications other than the investigational product**

The use of the investigational product used in this study as well as medications other than a topical anesthetic for nasogastric tube placement and acetylsalicylic acid used as needed is prohibited from 7 days before the start of administration of the investigational product until the completion of end-of-study assessment. However, this does not apply if the investigator (or subinvestigator) determines that it is necessary, such as for the treatment of adverse events.

(2) Smoking and intake of foods and drinks containing specific components

- Smoking or use of any products containing nicotine, alcohol, xanthin, caffeine, or grapefruit: from 24 hours before screening and each visit on Day -1 until hospital discharge.
- Use of any supplements: from 7 days before the start of investigational product administration until the end-of-study assessment.
- Foods or drinks containing poppy seeds: From 72 hours before screening and the hospitalization assessment until completion of prescribed assessment.

[Rationales for setting]

In order to perform pharmacokinetic assessment appropriately, the use of medications other than the investigational product, smoking, drinking alcohol, and intake of some foods are prohibited. This does not apply if the investigator (or subinvestigator) deems it necessary to use medications other than the investigational product, considering safe and ethical performing of this study.

Use of acetylsalicylic acid is permitted because it has been confirmed that there is no reporting that acetylsalicylic acid has inhibiting or inducing effects on sulfate conjugating enzymes and glucuronide conjugating enzymes, which are involved in edaravone elimination.

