12 CRITERIA AND PROCEDURES FOR SUBJECT WITHDRAWAL

12.1 Criteria for Subject Withdrawal

A subject will be withdrawn from the study if any of the following criteria is met.

- (1) The subject requests to withdraw from the study.
- (2) The subject is determined to be clearly ineligible as a study subject.
- (3) Study continuation becomes difficult for the subject due to the onset of an AE.
- (4) Other cases where the investigator (or subinvestigator) judges that the subject should be withdrawn from the study.

[Rationales for setting]

These criteria were established to perform the study ethically and to ensure the safety of the subjects.

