8.3.3 Analysis of Variance

AUC_{0-t} , $AUC_{0-\infty}$ and C_{max} of unchanged edaravone will be log transformed and analysed. Only subjects with the parameter value under both treatments will be analysed. Analysis of variance (ANOVA) will be used for analysis. Group, treatment, period and subject (nested in group) will be set to factors. Least squares (LS) means for each treatment will be calculated. These values will be back-transformed and shown in table. The difference of LS means between treatments (nasogastric administration minus oral administration) and 90% CI will be calculated. These values will be back-transformed, so that they show the ratio and 90% CI of PK parameters for nasogastric administration compared to oral administration.

As reference, the other pharmacokinetic parameters of unchanged edaravone will be analysed in the same way, although t_{max} will not be log transformed prior to the analysis.

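### Does the different wording on acetylsalicylic acid in exclusion criterion (13) and section 8.5.1(1) threaten the NGT/oral comparison?

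*Protocol*

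**What the plan says.** Criterion (13) in protocol section 3.3, repeated word for word in the synopsis, excludes "Subjects who have used any drugs other than the single use of acetylsalicylic acid within 7 days before the initiation of investigational product administration". The rationale under section 3.3 says only that this criterion, with several others, was set to protect the PK assessment. It does not explain the word single.

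Section 8.5.1(1) deals with medication from the same starting point up to the end-of-study assessment. Use of "medications other than a topical anesthetic for nasogastric tube placement and acetylsalicylic acid used as needed is prohibited from 7 days before" dosing begins. The rationale that follows permits acetylsalicylic acid because "it has been confirmed that there is no reporting that acetylsalicylic acid has inhibiting or inducing effects on sulfate conjugating enzymes" or on glucuronide conjugating enzymes. It draws no line between one use and several. The prohibition also yields where the investigator judges a medication necessary.

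Four other provisions decide what the difference can do:

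- Section 8.2, on dosing: "The investigational drug will be administered to subjects who meet all of the inclusion criteria and none of the exclusion criteria".
- Section 8.2, on reserves: "If any subject is excluded due to ineligibility prior to investigational drug administration", the reason is logged and a reserve subject takes the place.
- Section 12.1(2), on withdrawal: "The subject is determined to be clearly ineligible as a study subject".
- SAP section 8.3.3, on the primary analysis: "Only subjects with the parameter value under both treatments will be analysed".

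**The concern.** Two sections set different limits on the same drug over the same days, neither refers to the other, and the phrase in criterion (13) is not defined. A subject who uses acetylsalicylic acid more than once in the week before first dosing complies with 8.5.1(1) yet meets an exclusion criterion. The stated rationales do not settle the point.

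The worry for the analysis runs as follows. Suppose repeat use came to light only after the Period I dose. The subject might then be withdrawn as ineligible under 12.1(2). The reserve rule in 8.2 covers exclusion before dosing only, and the ANOVA keeps only subjects with values under both treatments, so that subject's pair would drop out of the NGT/oral comparison. A reader who relied on 8.5.1(1) would have kept the subject. On that account the wording affects who completes, and through that the precision of the ratio.

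**Working it through.** The plan states no figure on this point, so the check sets the provisions side by side.

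1. **Do the windows overlap?** Criterion (13) covers the seven days before first dosing. Section 8.5.1(1) starts seven days before first dosing and runs to the end-of-study assessment. The overlap is the whole of the seven pre-dose days.

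2. **Do the limits conflict?** One as-needed use satisfies both sections. More than one satisfies 8.5.1(1) and, if single is read as once, meets criterion (13). If the undefined phrase means occasional use, there is no conflict. The texts differ, and the documents do not say which reading is meant.

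3. **Does the protocol still say who is dosed?** Yes. Section 8.2 makes dosing depend on meeting none of the exclusion criteria. Compliance with 8.5.1(1) is not an exemption from section 3.3. An eligibility criterion can be narrower than a conduct rule that continues through the study, and a subject must pass both. This describes how the document operates. It does not say which limit the sponsor should keep.

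4. **When would repeat use be found?** Section 9.2.1.2 has the criteria confirmed at screening, at hospitalization and before the first administration. Section 8.6.2(8) requires subjects to report prescribed, purchased or planned drug use from consent onward. The concomitant-medication record in 9.2.2 starts only at dosing, so pre-dose detection rests on these two provisions. Use found at that stage leads to replacement under 8.2, and no pair is lost.

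5. **What if it is found later?** Section 12.1(2) requires the subject to be clearly ineligible. Where two sections of the same protocol disagree, that description is open to question, so withdrawal is not automatic.

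6. **Could it bias the ratio?** The use in question precedes the Period I dose. Which route a subject receives in Period I is randomized, 18 to each sequence, so such use has no systematic link to NGT or oral dosing. The ANOVA also includes period and subject nested in group.

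7. **What does the sample size absorb?** Section 6.1 plans 36 subjects for 30 completers, allowing 6 dropouts. If k subjects were lost for this reason and none for any other, 36 − k pairs remain. That is 35 for k = 1 and 30 for k = 6, so the planned number of completers is still met at k = 6. The documents support no value of k.

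**The case for a change.** The strongest opposing case is that site staff have to apply criterion (13) while instructions drawn from 8.5.1(1) tell subjects as-needed use is acceptable, so two staff members could classify the same subject differently. The case then puts a price on the lost pairs. The half-width of the 90% interval on the log scale is proportional to t(0.95, n1+n2−2) × √(1/n1+1/n2):

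- 18/18: 1.6909 × 0.3333 = 0.5636.
- 18/17: 1.6924 × 0.3382 = 0.5724, a ratio of 1.015.
- 15/15: 1.7011 × 0.3651 = 0.6212, a ratio of 1.102.

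A single lost pair would widen the interval by about 1.5%, and six by about 10.2%.

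The first part stands: a repeat user could be handled or recorded as a deviation differently depending on the section consulted. The second part is correct arithmetic attached to an unlikely chain. Each lost pair needs a repeat user who passes the pre-dose checks, is identified afterwards, is judged clearly ineligible and is not replaced. Six such subjects would be one in six of the 36. The 10.2% is also measured against full completion, whereas 30 completers is what the plan is built on. The figures show that fewer pairs give a wider interval. They do not show that this wording produces fewer pairs.

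The tube-placement anesthetic, exempt in 8.5.1(1) but not named in criterion (13), adds nothing. The protocol names it expressly as allowed, and SAP section 8.1.4 anticipates its use.

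**Conclusion.** The mismatch between criterion (13), its synopsis copy and section 8.5.1(1) is genuine but clerical. It can affect an individual eligibility decision or how a deviation is classified. No effect on the sample size, the precision or validity of the NGT/oral ratio, or safety has been shown. The expected statistical size is nil, because repeat use found before dosing leads to replacement by a reserve. In the extreme case of six post-dose losses and no other dropouts, the study still has its planned 30 completers.

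This rests on two assumptions: that sites apply section 8.2 as written and carry out the eligibility checks in 9.2.1.2, and that repeat use in the window is uncommon, since no document gives a count. The wording of the sections has to be reconciled, with the choice of limit left to the sponsor. That is copy-editing and calls for no change to the design or the analysis.

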4 EXPLANATION AND INFORMED CONSENT

4.1 Preparation of Written Information and Informed Consent Form

The investigator will prepare written information and the informed consent form (hereinafter referred to as informed consent form and written information). The informed consent form and written information will be a single document or a set of documents and subject to revision as needed.

The prepared and revised documents shall be submitted to the sponsor and approved by the institutional review board (IRB) prior to initiation of the study.

4.2 Contents of the Written Information

The written information for subjects should include explanations regarding the following:

- (1) That the study involves research.
- (2) Study Objectives
- (3) The name, title, and contact information of the investigator or subinvestigator.
- (4) Study methods (including experimental aspects of the study, inclusion criteria of subjects, and the probability of being allocated to active treatment if randomization is performed.)
- (5) That there is no intended benefit of the investigational product on the subject's mental and physical health, and foreseeable inconvenience to the subject.
- (6) The expected duration of the subject's participation in the study.
- (7) Participation in the study is based on the voluntary intention of the subject, and subjects can refuse or withdraw from participation in the study at any time. Subjects will receive no disadvantageous treatment due to refusal or withdrawal, and will suffer no loss of benefits by not participating in the study.
- (8) Source materials related to the treatment can be accessed by the monitor, auditor, Institutional Review Board and regulatory authorities. The privacy of the subject will be protected in such cases. By signing the informed consent form, the subject accepts such access.
- (9) If the results of the study are published, the subject's identity will remain confidential.
- (10) The person(s) to contact for further information regarding the study and the rights of study subjects, and whom to contact in the event of a study-related injury.
- (11) The compensation and treatment available to the subject in the event of a study-related injury.

- (12) The type of IRB that reviews and discusses the appropriateness of the concerned study, the matters to be reviewed and discussed at the IRB, and other study-related issues for the IRB.
- (13) The approximate number of subjects involved in the study.
- (14) That the subject will be informed in a timely manner if information becomes available that may be relevant to the subject's willingness to continue participation in the study.
- (15) The foreseeable circumstances and reasons under which the subject's participation in the study may be terminated.
- (16) The anticipated expenses, if any, to the subject for participating in the study.
- (17) The anticipated prorated payment, if any, to the subject for participating in the study (including the calculation method of the payment).
- (18) The subject's responsibilities.

4.3 Methods of Obtaining Informed Consent

- (1) Prior to the start of the study, the investigator (or subinvestigator) will provide each prospective subject with the informed consent form and written information approved by the IRB, as well as a thorough explanation regarding the study. Study collaborators can also give supplementary explanations to prospective subjects. The explanation provided to the prospective subjects should be expressed in plain words and expressions whenever possible so that he/she can easily understand the information. Each prospective subject must be given ample opportunity to inquire about the details of the study and receive answers to his/her satisfaction. The investigator (or subinvestigator) will obtain written consent to participate in the study from each prospective subject at his/her free will, after acquiring a thorough understanding.
- (2) The informed consent form should be signed and dated by the investigator (or subinvestigator) who has provided an explanation and the prospective subject. If a study collaborator has provided a supplementary explanation, he/she should also sign his/her name on the form with the date of entry.
- (3) Prior to each subject's participation in the study (at screening), the investigator (or subinvestigator) will issue the signed informed consent form with the date of entry, together with written information to the subject and retain the original, in accordance with the rules at the study site.
- (4) The date of obtaining informed consent should be recorded in Case Report Form.

4.4 Revision of the Informed Consent Form and Written Information

- (1) When any new and important information is obtained that may affect the consent of the subjects, the investigator (or subinvestigator) shall immediately provide the subjects with such information orally, confirm the intention of the subjects to continue participation in the study, and record the results in the medical records.
- (2) Based on the information in question, the investigator will promptly judge whether it is necessary to revise the informed consent form and written information.
- (3) When the investigator judges it necessary to revise the informed consent form and written information, he/she shall immediately perform these revisions and obtain approval from the IRB.
- (4) The investigator (or subinvestigator) will inform the subjects undergoing the study of such information using the informed consent form and written information that has been newly-approved by the IRB, and obtain a freely given written consent from each subject to continue participation in the study.
- (5) The form will be signed and dated by the investigator (or subinvestigator) who has provided an explanation and the subject will sign or write their name and affix a seal with the date of entry in the same manner as the first consent. If a study collaborator has provided a supplementary explanation, he/she should also sign his/her name on the form with the date of entry.
- (6) The investigator (or subinvestigator) will issue a signed informed consent form with the date of entry, together with written information to the subject and retain the original, in accordance with the rules at the study site.

